### 6.6.6. Simple Endoscopic Score for CD

The SES-CD ([Appendix E](#)) is a validated endoscopic index that closely correlates with the Crohn's Disease Endoscopic Index of Severity and is often considered the standard for endoscopic evaluation in subjects with CD. However, the SES-CD is considered more suitable for clinical trials due to its simplicity and has been widely adopted for this purpose ([Daperno, 2004](#)).

## 6.7. Corticosteroid Tapering Procedure

Subjects are eligible to start corticosteroid tapering beginning at the Week 12 Visit, at the discretion of the Investigator, according to the following schedule:

- For prednisone doses  $> 10$  mg (or equivalent), each week the daily dose is to be tapered by 5 mg until a dose of 10 mg/day is reached, after that each week the daily dose is to be tapered by 2.5 mg until discontinuation.
- For prednisone doses  $\leq 10$  mg (or equivalent), each week the daily dose is to be tapered by 2.5 mg until discontinuation.
- Subjects receiving budesonide should have their daily dose tapered by 3 mg every 3 weeks.

[Redacted text block]

[Redacted text block]

[Redacted text block]

[Redacted text block]

[Redacted text block]

CEL GENE PROPRIETARY INFORMATION

[Redacted text block]

[Redacted text block]

[Redacted text block]

[Redacted text block]

[Redacted text block]

CEL GENE PROPRIETARY INFORMATION

[Redacted]

[Redacted]

[Redacted]

CELGENE PROPRIETARY INFORMATION

## 7. DESCRIPTION OF STUDY TREATMENTS

### 7.1. Description of Investigational Product(s)

GED-0301 will be provided as 40-mg film coated tablets. Placebo will be provided as identically appearing tablets.

### 7.2. Treatment Administration and Schedule

Subjects will receive GED-0301 (160 mg QD) or placebo during the first 12 weeks of the study, followed by one of 3 dose regimens of GED-0301 (40 mg QD or 160 mg QD) or placebo QD, until the end of the study (Week 52 Visit). All subjects will receive 4 tablets daily during the Double-blind Treatment Period. Matched placebo tablets will also be provided. Subjects will be instructed to take the IP in the morning, 30 minutes before breakfast, with a glass of water. Treatment and administration schedule are described in [Table 4](#).

Subjects who consent to participate in the PK substudy will be instructed to bring their IP to the study site where it must be administered after the collection of the predose PK blood sample. When the subject is providing a predose blood draw on the day of a PK substudy visit, the subject must be reminded to provide the date and time of his/her last dose from the day before the visit.

#### 7.2.1. Dose Modification or Interruption

Dose modification is not permitted. Subjects will take their IP as determined by treatment arm. If a subject inadvertently does not take his or her medication for 4 or more consecutive days, Celgene or a Celgene designee must be contacted to decide whether the subject may remain in the study. Any inadvertent interruption in IP schedule will not alter the current dose or dose interval, nor will the length of the study be extended to account for days of IP missed. If a subject is unable or unwilling to restart IP at the prior dose and/or dose interval, then the subject will be evaluated by the Investigator for discontinuation from the Double-blind Treatment Period of the study, and enter the Follow-up Period.

#### 7.2.2. Overdose

Overdose, as defined for this protocol, applies to protocol-required dosing of the IP (GED-0301). Overdose for this protocol, on a per-dose basis, is defined as ingestion of more than 4 tablets of GED-0301 (or matching placebo) within the same calendar day whether by accident or intentionally. Adverse events associated with an overdose must be collected on the AE page of the eCRF (see Section 10.1) for all overdosed subjects, but the overdose itself is not considered an AE. Other required or optional nonstudy drugs intended for prophylaxis of certain side effects, etc, are excluded from this definition.

### 7.3. Method of Treatment Assignment

Approximately 1064 subjects will be randomized in a 1:1:1:1 ratio (266 subjects per GED-0301 arm [total 798]; 266 subjects in the placebo arm) to receive double-blind, oral GED-0301 or

identically appearing placebo QD for 52 weeks. The total number of subjects with a total SES-CD score  $\geq 6$  is targeted to comprise approximately 80% of the study population.

Subjects will receive double-blind, oral GED-0301 or identically appearing placebo daily (QD) as follows (Table 4):

- GED-0301 160 mg QD for 12 weeks; followed by placebo QD for 4 weeks; followed by alternating GED-0301 160 mg QD for 4 weeks and placebo QD for 4 weeks, until the Week 52 Visit;
- GED-0301 160 mg QD for 12 weeks; followed by placebo QD for 4 weeks; followed by alternating GED-0301 40 mg QD for 4 weeks and placebo QD for 4 weeks, until the Week 52 Visit;
- GED-0301 160 mg QD for 12 weeks; followed by continuous GED-0301 40 mg QD, until the Week 52 Visit;
- Placebo QD until the Week 52 Visit.

Treatment assignment at baseline (Week 0/Visit 2) will be stratified via an IWRS based on concomitant use of corticosteroids (yes/no); concomitant use of immunosuppressants (eg, AZA, 6-MP, or MTX) (yes/no); and previous exposure to biologics (ie, infliximab, adalimumab, certolizumab or vedolizumab) (yes/no). The total number of subjects with previous exposure to biologics is targeted to comprise approximately 35% of the study population.

At the Week 12 Visit and thereafter, until the Week 52 Visit, subjects who meet the criteria for early escape (Table 7) may (a) continue in the study at the discretion of the Investigator based on the totality of clinical data, (b) enter the Long-term Active-treatment Study (GED-0301-CD-004), or (c) discontinue the study. Subjects who complete the GED-0301-CD-002 Study at the Week 52 Visit will have the option to enter the Long-term Active-treatment Study.

Designated study personnel at the investigational sites will be assigned password-protected, coded identification numbers, which give them authorization to access the IWRS to randomize subjects. The system will present a menu of questions by which the study personnel will identify the subject and confirm eligibility. When all questions have been answered, the IWRS will assign a randomization identification number. Confirmation of the randomization will be sent via fax to the investigational site, Celgene and/or its representative.

During the study visits, the pharmacy or authorized study personnel at the investigational site will dispense coded IP kits in accordance with the randomization number assigned by the IWRS.

**Table 4: IP Dispensing Schedule: Double-blind Treatment Period**

| Week 0
Week 4
Week 8 | Week 12       | Week 16        | Week 20       | Week 24        | Week 28       | Week 32        | Week 36       | Week 40        | Week 44       | Week 48        |
|-------------------------------------|----------------------|-----------------------|----------------------|-----------------------|----------------------|-----------------------|----------------------|-----------------------|----------------------|-----------------------|
| GED-0301
160 mg QD               | Placebo
QD        | GED-0301
160 mg QD | Placebo
QD        | GED-0301
160 mg QD | Placebo
QD        | GED-0301
160 mg QD | Placebo
QD        | GED-0301
160 mg QD | Placebo
QD        | GED-0301
160 mg QD |
|                                     | Placebo
QD        | GED-0301
40 mg QD  | Placebo
QD        | GED-0301
40 mg QD  | Placebo
QD        | GED-0301
40 mg QD  | Placebo
QD        | GED-0301
40 mg QD  | Placebo
QD        | GED-0301
40 mg QD  |
|                                     | GED-0301
40 mg QD | GED-0301
40 mg QD  | GED-0301
40 mg QD | GED-0301
40 mg QD  | GED-0301
40 mg QD | GED-0301
40 mg QD  | GED-0301
40 mg QD | GED-0301
40 mg QD  | GED-0301
40 mg QD | GED-0301
40 mg QD  |
| Placebo
QD                       | Placebo
QD        | Placebo
QD         | Placebo
QD        | Placebo
QD         | Placebo
QD        | Placebo
QD         | Placebo
QD        | Placebo
QD         | Placebo
QD        | Placebo
QD         |

IP = investigational product; QD= once daily.

#### **7.4. Packaging and Labeling**

GED-0301 tablets will be packaged in blister cards and or opaque high density polyethylene (HDPE) bottles fitted with induction seals and tamper evident child resistant caps. The label(s) for IP will include Sponsor name, address and telephone number, the protocol number, IP name, dosage form and strength (where applicable), amount of IP per container, lot number, expiry date (where applicable), medication identification/kit number, dosing instructions, storage conditions, and required caution statements and/or regulatory statements as applicable. Additional information may be included on the label as applicable per local regulations.

#### **7.5. Investigational Product Accountability and Disposal**

The Investigator, or designee, is responsible for taking an inventory of each shipment of IP received, and comparing it with the accompanying IP shipping order/packing list.

The Investigator, or designee, will verify the accuracy of the information on the form, sign and date it, retain a copy in the study file, and return a copy to Celgene.

The IP must be stored as indicated on the label. At the study site, all IP will be stored in a locked, safe area to prevent unauthorized access.

Celgene (or designee) will review with the Investigator and relevant site personnel the process for IP return, disposal, and/or destruction including responsibilities for the site versus Celgene (or designee).

#### **7.6. Investigational Product Compliance**

Study personnel will review the instructions printed on the package with the study subjects prior to dispensing the IP. Investigational product will be dispensed as noted in the Table of Events (Table 3). The subjects will be instructed to return the IP containers, including any unused IP, to the study site at each visit for tablet counts and reconciliation. Subjects will be asked whether they have taken their IP as instructed at each study visit. Any problems with IP compliance will be reviewed with the subject. If a subject misses 4 or more consecutive days of dosing, Celgene must be contacted to decide whether dosing should resume or whether the subject should be terminated from the study, and enter into the Follow-up Period.

Gross compliance problems (eg, missing 4 or more consecutive days of dosing or taking less than 75% of the doses between study visits) should be discussed with Celgene. Compliance is defined as taking between 75% and 120% of dispensed IP.

## 8. CONCOMITANT MEDICATIONS AND PROCEDURES

All medications (prescription and non-prescription), treatments, and therapies taken by the subject from screening throughout their entire participation in the study, including those initiated prior to the start of the study, must be recorded on the subject's source document and on the appropriate page of the eCRF. The dose, unit, frequency, route, indication, date the medication was started, and date the medication was stopped (if not ongoing) must be recorded.

### 8.1. Permitted Concomitant Medications and Procedures

The following medications are allowed during the study:

- Oral aminosalicylates (SSZ or 5-ASA compounds), provided that treatment has been given at a stable dose for at least 2 weeks prior to the Screening Visit. The dose of oral aminosalicylates must remain stable through the duration of the study or early termination from the study. If oral aminosalicylates have been recently discontinued, treatment must have been stopped at least 2 weeks prior to the Screening Visit.
- Oral corticosteroids, provided that the dose (prednisone  $\leq$  20 mg/day or equivalent, budesonide  $\leq$  9 mg/day) has been stable for 3 weeks prior to the Screening Visit, and the dose must remain stable until the subject is eligible to start corticosteroids tapering (Section 6.7). If oral corticosteroids have been recently discontinued, discontinuation must have been completed at least 3 weeks prior to the Screening Visit.
- Immunosuppressants, such as AZA, 6-MP, or MTX, provided that treatment was initiated  $\geq$  12 weeks prior to the Screening Visit, must be at a stable dose for  $\geq$  8 weeks prior to the Screening Visit and remain stable for the duration of the study. If immunosuppressants have been recently discontinued, discontinuation must have been completed at least 8 weeks prior to the Screening Visit.
- Antibiotics used for the treatment of CD (eg, ciprofloxacin, metronidazole), provided that the dose has been stable for at least 2 weeks prior to the Screening Visit. If antibiotics have been recently discontinued, discontinuation must have been completed at least 2 weeks prior to the Screening Visit.
- Acetaminophen and low-dose aspirin for cardiovascular prophylaxis are allowed.

**Note:** The dose of concomitant CD medications noted above may not be increased during the study. No new CD therapy can be prescribed once the subject has been screened in the study.

### 8.2. Prohibited Concomitant Medications and Procedures

The following concomitant medications are prohibited during the Double-blind Treatment Period of the study, Screening Visit (Visit 1) through the Week 52 Visit, or the ET Visit for subjects who discontinue prematurely during the study:

- Use of any biologics are prohibited during the study and must be discontinued at least 8 weeks or 5 elimination half lives of the biologic, whichever is longer, prior to the Screening Visit. (See Table 8 for elimination half-life timeframes for biologics.)

- Use of bile acid sequestrants (eg, cholestyramine) is prohibited during the study and must be discontinued at least 3 weeks prior to the Screening Visit.
- Use of mycophenolic acid, tacrolimus, sirolimus, cyclosporine, thalidomide or apheresis (eg, Adacolumn®) is prohibited during the study and must be discontinued at least 8 weeks prior to the Screening Visit.
- Use of topical treatments with 5-ASA or corticosteroid enemas or suppositories is prohibited during the study and must be discontinued at least 2 weeks prior to the Screening Visit.
- Use of IV corticosteroids is prohibited during the study and must be discontinued at least 2 weeks prior to the Screening Visit.
- Administration of total parenteral nutrition (TPN) is prohibited and must be discontinued at least 4 weeks prior to the Screening Visit.
- Chronic use of nonsteroidal anti-inflammatory drugs (NSAIDs) is prohibited.

In addition, subjects who require ileostomy, colostomy, any intestinal resection, or intra-abdominal surgery (related to CD) during the study will be discontinued from treatment.

### **8.3. Required Concomitant Medications and Procedures**

There are no required concomitant medications.

Required procedures include ileocolonoscopy.

## 9. STATISTICAL CONSIDERATIONS

### 9.1. Overview

Key elements of the statistical analyses for this study are described in this section; details will be documented in a Statistical Analysis Plan (SAP). The statistical analyses for this study will be the responsibility of the Biostatistics department of the sponsor or its designee.

This study will be conducted as a double-blind study with in-house blinding procedures. For the purpose of the final data analysis, the official, final Week 52 database will not be unblinded until medical/scientific review has been conducted, protocol violations have been identified, the data have been declared final and complete, and a SAP has been written and approved. The randomization schedule will be generated and implemented by the external vendor of the study interactive web response system (IWRS).

### 9.2. Study Population Definitions

The intent-to-treat (ITT) population will be the primary population for the efficacy analysis. The ITT population will consist of all subjects who are randomized and receive at least 1 dose of IP.

Subjects will be included in the treatment group to which they were randomized for the efficacy analysis using the ITT [REDACTED] populations.

The analysis of safety data in this study will be based on the safety population, which will consist of all subjects who are randomized and receive at least 1 dose of IP. Subjects will be included in the treatment group corresponding to the IP they actually received for the analysis using the safety population.

### 9.3. Sample Size and Power Considerations

With a total of approximately 1064 subjects and a randomization ratio of 1:1:1:1, this study will randomize approximately 266 subjects into each of the three GED-0301 treatment groups and the placebo group. For the efficacy analyses of the first 12 weeks of the study, the three GED-0301 treatment groups will be pooled, due to the same treatment of GED-0301 160 mg QD received during the first 12 weeks, and the treatment comparisons will be made between GED-0301 160 mg QD (approximately 798 subjects) and placebo. For the efficacy analyses beyond Week 12, the treatment comparisons will be made between each of the three GED-0301 treatment groups and placebo. The study sample size is driven by the comparison of each of the three GED-0301 treatment groups with placebo with respect to the proportion of subjects with ER-50 at Week 52. The sample size and power calculations (not accounting for multiplicity adjustment) at a 2-sided significance level of 0.05 are given in [Table 5](#).

**Table 5: Sample Size and Power Calculations**

| Endpoint   | Assumptions                               | Sample Size per Group                     | Power a |
|--|---|---|--------------------|
| Clinical remission (CDAI score < 150) at Week 12 | Placebo = 22%
GED-0301 160 mg QD = 36% | Placebo = 266
GED-0301 160 mg QD = 798 | 99%                |
| Clinical remission (CDAI score < 150) at Week 52 | Placebo = 22%
GED-0301 160 mg QD = 36% | Placebo = 266
Any GED-0301 group = 266 | 95%                |
| ER-50 at Week 52                                 | Placebo = 10%
Any GED-0301 group = 20% | Placebo = 266
Any GED-0301 group = 266 | 90%                |

CDAI = Crohn's Disease Activity Index; ER-50 = endoscopic response defined as a reduction of at least 50% in the SES-CD; QD = once daily; SES-CD = Simple Endoscopic Score for Crohn's Disease.

a All power calculations do not account for multiplicity adjustment and are based on a 2-group chi-square test at a 2-sided significance level of 0.05, using East™ 6.3.

#### 9.4. Background and Demographic Characteristics

Subjects' age, height, weight, and other continuous variables will be summarized using descriptive statistics, while sex, race and other categorical variables will be provided using frequency tabulations. Medical history data will be summarized using frequency tabulations by Medical Dictionary for Regulatory Activities (MedDRA) system organ class and preferred term.

#### 9.5. Subject Disposition

[figure not shown]
Subject disposition (analysis population allocation, entered, completed, discontinued, along with primary reason for discontinuation) will be summarized using frequency and percent. A summary of subjects enrolled by site will be provided. Protocol deviations/violations will be summarized using frequency tabulations.

#### 9.6. Efficacy Analysis

For the efficacy analyses of the first 12 weeks of the study, the three GED-0301 treatment groups will be pooled, due to the same treatment of GED-0301 160 mg QD received during the first 12 weeks, and the treatment comparisons will be made between GED-0301 160 mg QD and placebo. For the efficacy analyses beyond Week 12, the treatment comparisons will be made between each of the three GED-0301 treatment groups and placebo.

##### 9.6.1. Statistical Methods

Binary endpoints will be analyzed by the Cochran-Mantel-Haenszel (CMH) test stratified by the randomization stratification factors. Subjects who have insufficient data for response determination for the time point under consideration will be considered nonresponders for that time point.

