**Table 2: Study Endpoints**

| Endpoint  | Name                          | Description  | Timeframe |
|-----------|-------------------------------|--|-----------|
| Primary   | Efficacy (Clinical remission) | The proportion of subjects achieving clinical remission, defined as a CDAI score < 150, at Week 12 | Week 12   |
| Secondary | Efficacy                      | The proportion of subjects achieving clinical remission, defined as a CDAI score < 150, at Week 52 | Week 52   |

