## 11. DISCONTINUATIONS

Subjects can discontinue at any time at their own request or at the discretion of the investigator. Reasons for discontinuation of a subject from treatment include but are not limited to:

- Any safety reason (eg, adverse event, laboratory abnormality) which in the opinion of the Investigator or the sponsor (or designee) places the subject at significant risk should he/she continue participating in the study. Please refer to [Appendix O](#) for discontinuation criteria related to liver function test abnormalities.
- Surgical procedures related to Crohn's disease (eg, intestinal resection, ileostomy, colostomy, intra-abdominal surgery related to CD)
- Initiation of a biologic medication (eg, TNF- $\alpha$  blockers, natalizumab, vedolizumab, ustekinumab)
- Initiation of immunomodulatory agents for the treatment of CD, such as mycophenolic acid, tacrolimus, sirolimus, cyclosporine, thalidomide or apheresis (eg, Adacolumn®).

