### 5.3. Analysis Populations

#### 5.3.1. Intent-to-treat Population

The intent-to-treat (ITT) population will be the primary population for the efficacy analysis. The ITT population is defined to include all subjects who are randomized and receive at least 1 dose of IP.

Due to the early termination of the study, for binary efficacy endpoints, the denominator at the time point under consideration will include subjects who have either completed that time point

or discontinued at any time due to reasons other than “study terminated by sponsor”, instead of all subjects included in the ITT population (Section 11.2.2.1).

Subjects will be included in the treatment group to which they were randomized for the efficacy analysis using the ITT population.

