### 11.2. Missing Data Handling

#### 11.2.2. Binary Efficacy Endpoints

##### 11.2.2.1. Primary Approach for Analysis

For binary efficacy endpoints, the primary approach to handling missing data will be nonresponder imputation (NRI), where subjects who are included in the denominator at the time point under consideration but have insufficient data for response determination at that time point will be considered nonresponders for that time point.

To eliminate the downward bias to the estimate of a binary endpoint due to the inclusion of subjects (as nonresponders due to NRI) who have not had a chance to reach the time point under consideration but have discontinued due to “study terminated by sponsor”, the denominator at

the time point under consideration will include subjects who have either completed that time point

or discontinued at any time due to reasons other than “study terminated by sponsor”, instead of all subjects in the ITT population.

[Redacted]

[Redacted]

[Redacted]

[Redacted]

[Redacted]

The within-group proportion, standard error (SE), and 2-sided 95% CI [REDACTED] for the within-group proportion will be provided for placebo, GED-0301 treatment regimens, and GED 160 (combining all 3 GED-0301 treatment regimens). The treatment comparison will be made between GED 160 and placebo. The unstratified treatment difference in proportions, stratified treatment difference in proportions using the weighted average of the treatment differences across the strata with the Cochran-Mantel-Haenszel (CMH) weights, stratified 2-sided 95% CI [REDACTED] for the treatment difference in proportions, and the 2-sided p-value from the CMH test stratified by the randomization stratification factors, will be provided for the comparison of GED 160 and placebo.

[REDACTED]

[REDACTED]

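### The stated nonresponder rule covers missing data only, so a subject who starts or increases corticosteroids, stays in the study and has CDAI below 150 is counted as a remitter

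*Protocol*

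**What the plan says.** - **Endpoint.** Protocol Table 2 defines the primary endpoint as "The proportion of subjects achieving clinical remission, defined as a CDAI score < 150, at Week 12". Appendix B (Table 7) repeats the CDAI cut-off. Neither mentions medication.
- **Nonresponse.** Protocol 9.6.1, and the statistical paragraph of the Protocol Summary, state: "Subjects who have insufficient data for response determination for the time point under consideration will be considered nonresponders for that time point". SAP 11.2.2.1 applies nonresponder imputation to subjects in the denominator who "have insufficient data for response determination at that time point will be considered nonresponders for that time point".
- **Denominator.** Under SAP 5.3.1 it consists of subjects who completed the time point "or discontinued at any time due to reasons other than “study terminated by sponsor”, instead of all subjects included in the ITT population".
- **Conduct rules.** Protocol 8.1 states "The dose of concomitant CD medications noted above may not be increased during the study" and "No new CD therapy can be prescribed once the subject has been screened in the study". Section 8.2 prohibits IV corticosteroids, topical 5-ASA or corticosteroids, bile acid sequestrants and biologics, among others.
- **Stopping treatment.** Protocol Section 11 lists "Initiation of a biologic medication", certain immunomodulatory agents and Crohn's-related surgery. It does not name a corticosteroid start or increase. The list is expressly open-ended.
- **Corticosteroid status in an endpoint.** It enters only one visible endpoint: Week 52 corticosteroid-free remission among subjects on oral corticosteroids at baseline.
- **Deviations.** Protocol 9.5 and SAP Section 7 summarise or list them. No visible text gives them a consequence for the endpoint.

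**The concern.** A conduct rule says what should not happen. It does not say how a subject is scored when it happens anyway. In Crohn's disease, corticosteroids can lower the CDAI whatever the study drug does. If a rescued subject remains in follow-up and has a complete CDAI below 150, the stated rule has no ground for calling that subject a nonresponder.

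The primary Week 12 comparison, Week 12 clinical response, Week 52 remission and sustained remission would then carry an unknown amount of rescue effect. The same rule governs the SES-CD binary endpoints. The trial was stopped early, but the SAP still reports these proportions and treatment differences with confidence intervals and p-values, so their meaning still matters.

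**Working it through.** **1. Follow the text for each kind of event.**

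| Event | Named in Section 11? | Usual path | Score under the stated rule |
|---|---|---|---|
| Oral corticosteroid start, or dose above baseline | No | May stay in the study | Decided by CDAI or SES-CD |
| IV corticosteroids (prohibited in 8.2) | No | May stay in the study | Same |
| Raised immunosuppressant, aminosalicylate or antibiotic dose; topical therapy; bile acid sequestrant | No | May stay in the study | Same |
| Biologic or listed immunomodulator | Yes | Treatment stopped, ET Visit (6.3) | Later data normally missing, so nonresponder |
| Crohn's-related surgery | Yes (also 8.2) | Same | Same |

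In the last two rows a gap remains if the event falls shortly before a Week 12 Visit that is still completed, or if the subject is not in fact withdrawn.

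**2. Reproduce the planned power.** Inputs are from Protocol Table 5: 22% v 36%, two-group chi-square, two-sided 0.05, 266 per arm, 798 v 266 at Week 12. The formula is power = Φ[(d − 1.96·se0)/se1], where se0 uses the pooled rate and se1 the separate rates.

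- Week 52 remission: se0 = √(0.29 × 0.71 × 2/266) = 0.0393; se1 = √((0.1716 + 0.2304)/266) = 0.0389. Power = Φ[(0.14 − 0.0771)/0.0389] = 94.7% (stated 95%).
- Week 12 remission: pooled rate = (266 × 0.22 + 798 × 0.36)/1064 = 0.325; se0 = 0.0332; se1 = 0.0306. Power = Φ[(0.14 − 0.0650)/0.0306] = 99.3% (stated 99%).
- ER-50, 10% v 20%: 90.0% (stated 90%).

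The stated powers are correct and are not in dispute.

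**3. Illustrate what the rule could do.** The documents give no rescue rate and no remission rate after rescue. Assume that 22% and 36% are the rates with rescued subjects as nonresponders, that 5–15% of placebo and 3–8% of GED-0301 subjects are rescued, and that a common 30–50% of them become counted remitters. Then counted rate = planned rate + rescued fraction × share. All eight corners:

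| Placebo / GED rescued | Share | Counted rates | Difference (points) | Week 12 power | Week 52 power |
|---|---|---|---|---|---|
| 5% / 3% | 30% | 23.5 v 36.9 | 13.4 | 98.6% | 92.2% |
| 5% / 3% | 50% | 24.5 v 37.5 | 13.0 | 97.9% | 90.2% |
| 5% / 8% | 30% | 23.5 v 38.4 | 14.9 | 99.6% | 96.2% |
| 5% / 8% | 50% | 24.5 v 40.0 | 15.5 | 99.7% | 97.1% |
| 15% / 3% | 30% | 26.5 v 36.9 | 10.4 | 88.3% | 73.3% |
| 15% / 3% | 50% | 29.5 v 37.5 | 8.0 | 66.1% | 49.8% |
| 15% / 8% | 30% | 26.5 v 38.4 | 11.9 | 95.0% | 83.6% |
| 15% / 8% | 50% | 29.5 v 40.0 | 10.5 | 87.5% | 72.1% |

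The difference can shrink or grow. Adding 5 points to both arms leaves 14 points, with power of 98.8% and 92.8%.

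**4. Reverse the premise.** Suppose 22% and 36% are already the rates under the stated rule. The present rule then costs no planned power, and scoring rescue as nonresponse subtracts from each arm. Removing 6 points from placebo and 2 from GED-0301 gives Week 52 power of 99.8%. Removing 2 and 6 gives 76.1%.

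**The case against.** **The rule may exist out of sight.** Protocol 9.1 says Section 9 gives only the main elements and leaves detail to the SAP. SAP 11.2.2.1 has redacted blocks directly after the imputation and denominator text. The SAP time-point section, its list of changes and the protocol text after the taper schedule (6.7) are also partly redacted. This stands: the point can be made only about the visible text, and a reader should not infer that the SAP certainly lacks a treatment-failure rule.

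**Discontinuation and early escape catch most cases.** For biologics, listed immunomodulators and surgery this is largely right, so the inference that any prohibited Crohn's therapy can produce a counted remitter is too broad. It does not settle corticosteroids. An open list permits withdrawal but does not require it, and subjects who meet the early-escape criteria may continue at the investigator's discretion.

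**Counting everyone by observed CDAI is legitimate.** A treatment-policy reading fits the primary objective, which asks only about clinical activity at Week 12 against placebo. That is fair, but no visible text says this choice was made, and the conduct rules bar the therapies it would absorb.

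**Rescue should be commoner on placebo, so the rule dilutes the effect.** A reader might infer this. It is plausible, but the documents contain nothing to support it, and more rescue on GED-0301 would inflate the effect.

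**Conclusion.** The point holds in limited form. As written, a subject who starts or increases corticosteroids, or receives other barred Crohn's therapy that does not lead to withdrawal, and who stays in the study is scored on observed CDAI or SES-CD alone at Week 12 and Week 52. The exception is the corticosteroid-free endpoint in baseline users. For biologics, listed immunomodulators and surgery only the residual gap shown in the working remains.

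The consequence is an estimate that mixes drug and rescue effects. Its size and direction are unknown. Under the assumed ranges the 14-point difference becomes 8.0 to 15.5 points and nominal Week 52 power 50% to 97%. These figures show sensitivity to unequal rescue and are not a forecast. They do not show that Table 5 is wrong, and after early termination planned power matters less than what the reported estimates mean. The finding rests on the visible text and falls away if a redacted passage already scores these events.

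**What to change.** Unless the redacted SAP text already does so, add to SAP 11.2.2.1, consistently with Protocol 9.6.1, a rule for the CDAI and SES-CD binary endpoints. A subject who, before a time point, started corticosteroids or exceeded the baseline dose, or received new or prohibited Crohn's therapy, is a nonresponder at that time point and all later ones. Keep the data-only rule as a sensitivity analysis, and report by arm how many subjects the new rule reclassifies. If a redacted rule exists, a cross-reference is enough.

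This is an analysis definition and leaves clinical management unchanged. Protocol Section 8 already requires dose and start and stop dates of all medications in the eCRF, so no new data are needed. The cost is SAP wording, some programming and slightly lower absolute rates.
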